4.2. Secondary Objective

Blood pressure and antihypertensive medication related

1. To compare the mean change in systolic and diastolic blood pressure between the 2 groups from baseline to 6 months and 2 years post randomization
2. To compare the proportion of patients having adequate control of hypertension at end of 1 year and 2 years

3. Among those with adequate control, to compare the de-escalation of dose or reduction in the number of antihypertensive medications from baseline to 6 months, 1 year and 2 years in both the groups
4. To study the frequency of introduction of new antihypertensive medications or dose escalation of existing antihypertensive medications in both the groups

Metabolic parameters and biomarkers based

5. To study the effect of Twin Precision treatment on change on metabolic parameters
6. To study the effect of Twin Precision treatment on change in cardiac and renal biomarkers

Quality of life and Safety related

7. To study the safety of Twin Precision treatment on antihypertensive drug withdrawal
8. To compare the change in quality of life and treatment satisfaction between the 2 groups

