Moderation of alcohol consumption and smoking cessation	
Counselling will be provided on the importance of cessation of smoking and alcohol consumption. Habitual drinkers will be advised on the moderation of amount and to avoid binge drinking. The recommended daily limit for alcohol consumption is 2 standard drinks for men and 1.5 for women (10 g alcohol/standard drink).

Management of blood pressure in standard care arm

Medication will be started or up titrated if blood pressure is > 140/90 mm Hg and treated to reach target blood pressure

Target blood pressure control will be(10)

Office

- In <65 years < 130/80 mm Hg
- In 65 and above < 140/90 mm Hg

ABPM

- 24 hr average \leq 130 and/or \leq 80
- Day time average \leq 135 and/or \leq 85
- Night time average \leq 120 and/or \leq 70

HBPM \leq 135 and/or \leq 85

Frequency of assessment: For patients in the standard care arm, blood pressure will be assessed monthly after initiation or change in antihypertensive medication until target blood pressure is reached. Subsequently blood pressure will be monitored every 3 monthly.

Standard care home based BP monitoring: Self-measured BP monitoring be based on 2 measurements taken at least 1 minute apart in the morning and evening (ie, 4 readings per day) optimally for 7 days (ie, 28 readings total) with a minimum of 3 days (ie, 12 readings total). For each monitoring period, the average of all SBP and DBP readings should be obtained to assess BP. If the first day's readings are excluded, the preferred and minimum periods of monitoring should be 8 and 4 days, respectively. (9)

Standard care Office based BP monitoring:y 2–3 office visits at 1–4-week intervals. At each visit take 3 measurements with 1 min between them. Calculate the average of the last 2 measurements. If BP of first reading is <130/85 mmHg no further measurement is required.(10)

Stepwise approach for use of antihypertensive medications

Consider monotherapy in low risk grade 1 hypertension or in very old (> 80 yrs).

Category	Systolic		Diastolic
Normal BP	<130	and	<85
High normal BP	130-139	and/or	85-89
Grade 1 hypertension	140-159	and/or	90-99

Grade 2 hypertension	≥ 160	and/or	≥ 100
----------------------	-------	--------	-------

Table-1 Grades of hypertension

Classification of hypertension risk based on risk factors, end organ damage. (Table-2)

Risk factors/ Hypertension mediated organ damage	High normal blood pressure	Grade 1 hypertension	Grade 2 hypertension

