Dose reduction or withdrawal of antihypertensive drugs will be considered when the patient reaches the target blood pressure. The dose reduction is in accordance with the protocol described by Nelson et al. i.e half dose reduction at weekly intervals with weekly assessment until the lowest dose is reached followed by withdrawal. The period of withdrawal will range from 2 weeks to 4 weeks.

Target blood pressure for our study will be considered as 130/80 mm Hg for young individuals and 140/90 mm Hg for elderly (65 and above) -2020 International Society for Hypertension Global Hypertension Practice Guidelines

Table-4 Antihypertensive medicines escalation and de-escalation protocol

Tier number	Medicines	Initial condition on enrolment	Reduction condition	Increase conditions
Tier 0	No medicine	Initial no medicine & BP < 160/100 mm Hg		Move to Tier 1, if (5d-BP > 135/85) & (after staying in this tier for 5 days)
Tier 1	Monotherapy (A)	Monotherapy	Move to Tier 0, if ((1d-BP < 135/85 for 7 consecutive days) II (1d-BP < 90/60 for 3 consecutive days) II (Symptoms of Hypotension like Postural Giddiness)) && (EOD-)	Move to Tier 2, if (5d-BP > 135/85) && (after staying in this tier for 5 days)
Tier 2	Dual low dose combination (A+C)	Dual low dose combination	Move to Tier 1, if ((1d-BP < 135/85 for 7 consecutive days) II (1d-BP < 90/60 for 3 consecutive days) II (Symptoms of Hypotension like Postural Giddiness))	Move to Tier 3, if (5d-BP > 135/85) && (after staying in this tier for 5 days)

Tier 3	Dual full dose combination (A+C)	Dual full dose combination/ Triple combination/ Triple combination + spironolactone or Alpha blocker	Move to Tier 2, if ((1d-BP < 135/85 for 7 consecutive days) II (1d-BP < 90/60 for 3 consecutive days) II (Symptoms of Hypotension like Postural Giddiness))	Move to Tier 4, if (5d-BP > 135/85) && (after staying in this tier for 5 days)
Tier 4	Triple combination (A+C+B/ D/ Alpha blocker)	Triple combination/ Triple combination + spironolactone or Alpha blocker	Move to Tier 3, if ((1d-BP < 135/85 for 7 consecutive days) II (1d-BP < 90/60 for 3 consecutive days) II (Symptoms of Hypotension like Postural Giddiness))	Consider manual change of medication or withdraw

A= ACE inhibitor or ARB

C = Calcium channel blocker

B = Beta blocker

D = Diuretics

Note:

- EOD (End organ damage) + =
1. LVH present
 2. Albuminuria
 3. Evidence of Heart failure
 - A. Low ejection fraction
 - B. High pro-BNP
 - C. Clinical features
 4. Hypertensive retinopathy

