9.2 Secondary outcome

Blood pressure and antihypertensive medication related

1. **Change in blood pressure (Clinical and ambulatory blood pressure)** from baseline to 6 months and 2 year. Ambulatory and clinic blood pressure monitoring will be done as mentioned in the primary endpoint.
2. **Adequate control of blood pressure** as measured by ambulatory blood pressure monitoring at 1 year and 2 years

Criteria for adequate control of blood pressure is

- In <65 years < 130/80 mm Hg
- In 65 and above < 140/90 mm Hg

3. Number of antihypertensive medications at 6 months, 1 year and 2 years

Among those with adequate control, the number of antihypertensive medications will be calculated at baseline (after run in period) and subsequently every 3 months. Combination pills containing more than one group (of antihypertensive medications) will be considered based on the number of groups. Example: Lotrel which is a combination of Amlodipine and benazepril will be considered as 2 drugs. Further each drug will be categorized as high dose or low dose.

Table-5 for doses of commonly used antihypertensive medications

Drug name	Dose 1	Dose 2	Dose 3	Dose 4
Losartan	25 mg	50 mg		
Telmisartan	20 mg	40 mg	80 mg	
Olmesartan	5 mg	20 mg	40 mg	
Candesartan	16 mg	32 mg		
Captopril	12.5 mg	25 mg	50 mg	100 mg
Enalapril	5 mg	10 mg	20 mg	40 mg
Lisinopril	5 mg	10 mg	20 mg	40 mg
Ramipril	1.25 mg	2.5 mg	5 mg	
Hydrochlorothiazide	12.5 mg	25 mg	50 mg	100 mg

Chlorthalidone	25 mg	50 mg	100 mg	
Indapamide	1.25 mg	2.5 mg	5 mg	
Frusemide	20 mg	40 mg		
Prazosin	1 mg	2.5 mg	5 mg	
Terazosin	1 mg	2 mg	5 mg	
Doxazosin	1 mg	2 mg	4 mg	
Propranolol	10 mg	20 mg	40 mg	
Metoprolol	25 mg	50 mg	100 mg	
Atenolol	50 mg	100 mg		
Bisoprolol	5 mg	10 mg		
Amlodipine	5 mg	10 mg		
Cilnidipine	5 mg	10 mg	20 mg	
Nicardipine	20 mg	40 mg	80 mg	
Nifedipine	30 mg	60 mg	90 mg	
Felodipine	2.5 mg	5 mg	10 mg	

4. Frequency of introduction of new antihypertensive medications or dose increment of existing antihypertensive medications will be noted across both the groups and compared.

Metabolic parameters and biomarkers based

5. Change in metabolic parameters

- Will include anthropometric assessment (Height, Weight, BMI, waist circumference, Waist hip ratio, visceral fat), lipid profile including lipoprotein (a), apolipoprotein - A1, apolipoprotein - B, insulin resistance (measured by HOMA- IR) every 3 months till end of study

6. Change in cardiac and renal biomarkers

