12.2 Statistical analysis plan

All quantitative variables will be assessed for the normality by Shapiro-Wilk's test. If they follow Gaussian distribution, then they will be expressed as mean + SD. Continuous or quantitative variables which wouldn't follow normal distribution, will be transformed into logarithms or square root. Again, normality will be assessed by Shapiro-Wilk's test. Those variables which will not be following normal distribution after transformation will be represented by median (Interquartile range). Qualitative variables will be expressed as counts and percentages. Analysis will be carried out for the Intention to treat population as well per protocol population. Missing observations will be handled with imputation techniques. Comparison of quantitative data between the intervention group and control group will be done by independent sample 't' test, if they follow normal distribution. Non-normally distributed quantitative variables will be compared by Mann-Whitney U test. Comparison of categorical variables between groups was done by either Chi-square test or Fisher's Exact test based on the number of observations available. ANOVA will be used to compare the mean of normally distributed continuous variables across more than two categories. Equivalent non-parametric test viz, Kruskal Wallis H test will be used to compare non normally distributed continuous variables. Paired 't' test or Wilcoxon Signed Rank test will be used to compare pre and post continuous variables within the groups based on their normality. Exploring the possibilities of doing regression models with covariates. Data capturing and automation will be taken care of by Tableau Software. Microsoft Excel will be used to cross validate the data collected. Data validation and analysis will be carried out by IBM SPSS Statistics for Windows Ver 28.0; Armonk; NY; IBM Corporation. For statistical significance, two tailed p values <0.05 will be considered.

13. Ethical considerations

Study will be initiated after ethics committee approval and after obtaining written informed consent.

Possible benefits

The study may directly benefit the patient as well as the society. The anticipated benefits are improvement in blood pressure control, decrease in the number of antihypertensive

medications, body weight and complication rates of hypertension along with an overall improvement in the quality of life.

Risks involved

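### Secondary objective 3 and outcome 3 compare drug reduction only among patients with adequate control, a post-randomisation outcome, so randomisation does not protect the comparison

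*Protocol*

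**What the plan says.** Protocol 4.2, objective 3, sets the comparison: "Among those with adequate control, to compare the de-escalation of dose or reduction in the number of antihypertensive medications from baseline to 6 months", continuing to 1 year and 2 years in both groups. Protocol 9.2, item 3, repeats the restriction: "Among those with adequate control, the number of antihypertensive medications will be calculated at baseline (after run in period) and subsequently every 3 months".

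The only definition of adequate control given as an outcome is in 9.2, item 2, directly above. It uses age-specific thresholds (130/80 mm Hg under 65 years, 140/90 mm Hg from 65), "as measured by ambulatory blood pressure monitoring at 1 year and 2 years". Control is also compared between the arms under objective 2: "To compare the proportion of patients having adequate control of hypertension at end of 1 year and 2 years".

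Medication rules differ by arm. In the intervention arm (7.3.2), "Dose reduction or withdrawal of antihypertensive drugs will be considered when the patient reaches the target blood pressure", with a tiered step-down table. For standard care (7.3.1), "Medication will be started or up titrated if blood pressure is > 140/90 mm Hg", followed by a stepwise scheme for adding drugs.

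Two other places bear on the point. Item 4 of 9.2 carries no control restriction: "Frequency of introduction of new antihypertensive medications or dose increment of existing antihypertensive medications will be noted across both the groups and compared". Section 12.2 names the analysis sets: "Analysis will be carried out for the Intention to treat population as well per protocol population". The design synopsis lists the requirement for antihypertensive drugs as a secondary outcome, also without a restriction.

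**The concern.** Randomisation makes the arms comparable as randomised. It does not make comparable the subsets that later reach a blood pressure target. The protocol plans for a 5 mm Hg larger SBP reduction with the intervention (12.1), so it expects treatment to alter who is controlled. If the intervention brings harder-to-control patients under the threshold, its controlled subset is more severe on average than the standard-care subset. A difference in drug reduction between the subsets then mixes the treatment effect with that difference in case mix. Naming an intention-to-treat population in 12.2 does not help, because item 3 filters that population by a post-randomisation result.

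There is a second effect within the endpoint. Section 13 accepts that blood pressure may rise when drugs are tapered. A patient whose control is lost after tapering is no longer in item 3's denominator, so an unsuccessful de-escalation does not weigh against the successful ones there.

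Item 3 is the only endpoint that measures reduction of medication, and Section 13 lists fewer antihypertensives among the anticipated benefits. What is at stake is whether that result can be read as an effect of the randomised treatment.

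**Working it through.** **The plan's own figure.** The protocol gives no figure for the medication endpoint. For the primary SBP outcome it states 83 + 166 evaluable patients (difference 5, SD 13, power 80%, two-sided 5%, ratio 1:2). The normal approximation gives 80 + 160 and the t-test version 81 + 162, so the stated size is slightly generous; power at 83 + 166 is about 0.81. Dropout: 83/0.8 = 104 and 166/0.8 = 208, both as stated. Nothing below changes these numbers. They serve only as the starting headcount.

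**Illustration of the selection effect.** Only the 5 mm Hg effect comes from the protocol; the other inputs are assumed.
- Severity S ~ N(0,1), equal in both arms by randomisation.
- 1-year SBP = 132 + 10·S − 5·(intervention) + N(0, SD 6), so the SBP SD is √(100 + 36) = 11.66 and its correlation with S is r = 10/11.66 = 0.857.
- Drug reduction = 0.6 − 0.4·S + N(0, SD 0.8), with no arm effect.
- Control means SBP < 130.

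Control rates:
- Standard: Φ((130 − 132)/11.66) = Φ(−0.171) = 0.43
- Intervention: Φ((130 − 127)/11.66) = Φ(0.257) = 0.60

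Mean severity among the controlled is −r·φ(a)/Φ(a), where a is the standardised cut-off:
- Standard: −0.857 × 0.393/0.432 = −0.78
- Intervention: −0.857 × 0.386/0.602 = −0.55
- Gap: 0.23 SD

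Spurious difference in drug reduction among the controlled: −0.4 × 0.23 = −0.09 drugs (simulation: −0.089). Among all randomised patients it is 0.00. The sign is against the intervention.

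**Patients left in the comparison.**
- 166 × 0.60 ≈ 100 and 83 × 0.43 ≈ 36, total 136.
- Headcount: 1 − 136/249 = 45% lost.
- Effective size n₁n₂/(n₁+n₂): 83 × 166/249 = 55.3 before, 100 × 36/136 = 26.5 after; 1 − 26.5/55.3 = 52% lost.

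**How large the bias is against noise.** With 100 and 36 patients the standard error of the difference is about 0.17 drugs, so the bias is about 0.09/0.17 ≈ 0.5 standard errors. That lifts a nominal 5% two-sided error rate to about 8%.

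**Sensitivity.** A second set of assumptions used SBP SD 13, standard-arm mean 130 to 140 mm Hg, mean about 1.6 drugs, and a correlation of 0.2 to 0.6 between SBP and drug number. It gave control of 22–50% versus 35–65%. With no true effect, the controlled intervention patients took 0.04 to 0.14 more drugs. Both illustrations use the same mechanism, so their shared direction is not independent evidence of direction in this trial.

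**The case against.** The strongest reply has five parts.

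*The restriction has a clinical logic.* Fewer drugs with uncontrolled blood pressure is not a success. This stands. It is why a bare drug count in everyone should not be read alone, and why the fix pairs it with a composite that requires control. It does not justify defining the denominator by a result of treatment.

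*Failed de-escalation is recorded elsewhere.* A reader might infer that patients harmed by withdrawal vanish from the trial. They do not. Item 2 counts them as not controlled, item 4 counts drugs added or increased, and item 7 counts uncontrolled hypertension and related admissions. They leave item 3 only. Items 2, 4 and 7 do not repair item 3, because none of them measures reduction.

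*Adequate control might mean control at baseline.* The inclusion criteria use similar words for patients at entry, and item 3 starts counting at baseline. A baseline subgroup would be a valid comparison. But no baseline definition is attached to this outcome, and the definition directly above it is post-randomisation. If baseline was meant, the text still has to say so.

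*Control is not given as an outcome at 6 months.* A reader might infer that the subset cannot be formed then. That goes too far: the thresholds are stated generally, and ambulatory monitoring every 3 months after month 3 (7.5.1) allows control to be determined. Whether membership is fixed or reassessed at each visit is a detail a SAP commonly settles.

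*The bias is small and the endpoint secondary.* Both are fair, and they limit the severity.

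**Conclusion.** The point holds for objective 3 and outcome 3. As written, they give a comparison that randomisation does not protect, because entry depends on a post-randomisation outcome that treatment is expected to change. This follows from the text and needs no simulation.

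The size is not known. About 0.09 drugs (0.04 to 0.14 under the other assumptions), against the intervention, is an illustration. It rests on assumed mean SBP, severity and drug models and on a single systolic cut-off, ignoring the diastolic limit and the higher threshold from age 65. The losses of 45% in headcount and 52% in effective size rest on the assumed control rates of 60% and 43%.

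Two stronger readings are not supported. A reader might infer that the design is tilted to produce a false benefit; in the mechanism examined the bias runs the other way, and other mechanisms could reverse it. A reader might also infer that this endpoint is the main evidence for reversal of hypertension. Section 3 ties reversal to improved metabolic health, no section defines it by drug count, and the primary endpoint is blood pressure change. The point is therefore something that should be fixed in one secondary endpoint, not a threat to the trial's main conclusion.

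**What to change.** Reword 4.2 item 3 and 9.2 item 3 as follows.

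- Compare the change in number of antihypertensives and in dose category at 6 months, 1 year and 2 years in all randomised patients, adjusted for the baseline number.
- Read it together with a binary outcome in all randomised patients at the same time points: adequate control by the thresholds in 9.2 item 2, with fewer or lower-dose drugs than at baseline (yes or no). Patients who are not controlled count as no, which keeps the link with control without removing anyone from the denominator.
- Keep the controlled-only summary as descriptive, without a test between arms.

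The synopsis already lists the medication outcome without a restriction, so this also aligns the sections. The cost is wording plus a little extra analysis. Medication details are taken at baseline for every patient (7.1), and item 4 already needs follow-up drug records in both groups. The primary outcome and sample size are unaffected. The change should be made before outcome data are seen.

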4.3 Exploratory objective

1. To study the change in exploratory biomarkers between the 2 groups
 - Endothelial function based biomarkers
 - Stress based biomarkers
 - Inflammatory biomarkers
 - Hormones, Vitamins and minerals
2. To study the incidence of hypertension mediated organ damage (brain, heart, kidney, artery, eyes)

5. Study design: Multi centric, open label, parallel arm randomized controlled trial

[figure not shown]

Figure-1 Study design

Study period: The total study period will be for approximately 3 years as follows:

Run in period: 2-3 weeks

Intervention period: 2 year

Passive Follow up: 1 year

After screening, all eligible patients will have a mandatory 2-3 weeks run-in period with existing therapy (standard care) for stabilization of blood pressure and for baseline continuous glucose monitoring. Patients with blood pressure >180/110 mm Hg at the end of 3 weeks run-in period will be considered as screen failure.

Number of groups:

Group A (Standard care arm): Will receive medications for hypertension along with lifestyle modifications as per existing guidelines

Group B (Intervention arm): Will receive Twin Precision Treatment along with standard care

6. Eligibility criteria

Inclusion criteria

1. Patients with diagnosis of primary hypertension (either adequately controlled or inadequately controlled with blood pressure \leq 180/110 mm Hg); both treatment naive & on treatment (includes monotherapy or multiple drugs)
2. Age 18 years and above
3. Of either gender
4. Willing to follow study specific activities and able to handle smartphone

Exclusion criteria

Patients with the following criteria will be excluded.

1. Uncontrolled hypertension ($>$ 180/110 mm of Hg) or history of hypertensive emergency requiring admission
2. Hypertension due to secondary causes
3. History of Diabetes mellitus (when either of the following criteria is met: on medications to control blood sugar or FBS $>$ 126 mg/dl; RBS $>$ 200 mg/dl; HbA1c \geq 6.5)
4. Symptomatic heart failure or EF $<$ 40%
5. Chronic kidney disease (eGFR less than 60 ml/min/1.73 m²) or history of any major renal anomalies like unilateral kidney, polycystic kidney
6. Any major cardiovascular event in the last 6 months (such as MI, stroke, TIA)
7. Hypertensive Retinopathy (grade 3 and above)
8. Weight loss more than 5% in 3 months
9. Arm circumference too large or small to allow accurate BP measurement with available devices

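### The between-arm comparison of drug reduction (objective 3, outcome 3) reflects a strategy in which only Group B has a written step-down rule, so it cannot show that nutrition or better metabolism reduced the need for drugs

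*Protocol*

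**What the plan says.** **The comparison.** Objective 3 (Protocol 4.2) is restricted to adequately controlled patients of each arm and reads: "to compare the de-escalation of dose or reduction in the number of antihypertensive medications from baseline to 6 months, 1 year and 2 years". Outcome 3 (9.2) makes it operational: "Among those with adequate control, the number of antihypertensive medications will be calculated at baseline (after run in period) and subsequently every 3 months". The synopsis lists the need for antihypertensive drugs as a secondary outcome.

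**Group A (7.3.1).** The medication rule is: "Medication will be started or up titrated if blood pressure is > 140/90 mm Hg and treated to reach target blood pressure". Table 3 is a ladder for adding drugs. Review is monthly until target; after that, "Subsequently blood pressure will be monitored every 3 monthly". No condition for reducing or stopping a drug is written.

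**Group B (7.3.2).** "Dose reduction or withdrawal of antihypertensive drugs will be considered when the patient reaches the target blood pressure". Table 4, which the list of tables labels as belonging to the intervention arm, moves a patient down one tier when "1d-BP < 135/85 for 7 consecutive days" holds, or on very low readings or symptoms of hypotension. Moving from Tier 1 to Tier 0 also requires no end-organ damage. A patient moves up when the 5-day value exceeds 135/85 after 5 days in the tier.

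**Both arms.** Section 7.4 provides for monitoring after dose reduction in all patients but gives no trigger. Section 7.5 assigns home readings to dose titration, and 7.5.2 schedules them on five days each week. Inclusion criterion 1 admits patients who are "either adequately controlled or inadequately controlled", treated or untreated.

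**The concern.** The outcome is a prescribing decision, and the written rule for that decision differs by arm. Once a patient is controlled, Group B's text directs the team to consider taking drugs away, whereas Group A's text only extends the review interval. Restricting the outcome to controlled patients does not remove this, because those are the patients to whom the Group B rule applies.

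What is at stake is interpretation. Section 3 frames the trial as reversing hypertension by improving metabolism. The opening line of 7.3.2 describes Group B as nutrition added to standard medication. Section 13 lists fewer drugs among the expected benefits. With no stated limit, a lower drug count in Group B could be presented as a reduced need for drugs because metabolism improved, although some or all of it may come from one arm having a rule to taper.

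**Working it through.** No figure in the protocol bears on this outcome. The sample size in 12.1 concerns 1-year systolic pressure and is unaffected. The check is therefore a comparison of texts, followed by an illustration on assumed inputs.

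**1. Written rules side by side**

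| | Group A (7.3.1, Table 3) | Group B (7.3.2, Table 4) |
|---|---|---|
| Step up | Above 140/90, monthly and then 3-monthly review | 5-day value above 135/85 after 5 days in the tier |
| Step down | None written | Seven days below 135/85, very low readings, or symptoms |

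Read literally, no controlled Group A patient loses a drug under a written rule, while a controlled Group B patient can.

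**2. Can the Group B trigger fire with no programme effect?**

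Assumptions, none from the protocol: a patient enters controlled on drugs with mean home BP 125/75, daily SD 6/4 mm Hg, independent readings, systolic and diastolic treated as independent, and a programme effect of zero.

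- One day below 135/85: Φ(10/6) × Φ(10/4) = 0.952 × 0.994 = 0.946.
- Seven readings in a row: 0.9463^7 = 0.68.

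The first step-down is therefore likely in any given seven-reading window, although nothing about the patient has changed.

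**3. What follows the step-down?**

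Assume that losing a tier raises home BP by 5/3, to 130/78.

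- Step-up: the mean of five readings has SD 6/√5 = 2.68 and 4/√5 = 1.79. P(mean above 135 or above 85) = 1 − Φ(5/2.68) × Φ(7/1.79) = 0.031 per window. Over 52 weekly windows, 1 − (1 − 0.031)^52 = 0.81.
- Further step-down: [Φ(5/6) × Φ(7/4)]^7 = (0.798 × 0.960)^7 = 0.154 per window.

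This patient moves both ways during a year. The example shows that the trigger needs no programme effect. It does not show how lasting the reduction is.

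**4. Direction of the net difference**

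Three forces act: Group B's step-down rule lowers its drug count, Group B's lower and faster step-up threshold raises it, and any informal tapering lowers Group A's count. A one-year simulation with zero programme effect varied assumed entry pressure, variability, drug effect per tier and frequency of end-organ damage. It applied the 135/85 trigger to seven consecutive scheduled readings. Group B minus Group A, in percentage points of controlled patients on fewer drug classes:

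| Informal tapering in Group A (share of at-target visits) | Range |
|---|---|
| 0% | +3 to +38 |
| 10% | +2 to +34 |
| 30% | −7 to +28 |
| 50% | −19 to +23 |

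These ranges are conditional on assumed inputs. They show only that size and sign depend on a quantity the protocol does not fix.

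**5. The seven-day trigger**

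If the same five days are measured each week, the longest unbroken run is five days and the main trigger is never met (0%). Section 7.4 mentions twice-daily home readings, which may supply daily values once tapering has begun, but not before the first step-down.

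**The case against.** **The protocol does not make the attribution.** Objective 3 and outcome 3 compare arms without mentioning nutrition or metabolism. The synopsis and 7.3.2 include medicine in the Twin Precision programme, and objective 7 makes withdrawal under it a subject of study. This stands: the between-arm test is legitimate for the whole strategy. What remains is that the rationale and the short description of Group B invite the narrower reading and nothing excludes it.

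**Group A may taper too.** Guideline care leaves physicians free to reduce drugs, so no written trigger does not mean no reduction. This also stands. A reader might infer a known bias in favour of Group B; the documents do not support that, since every input to the ranges above is assumed and the sign can reverse.

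**The thresholds are consistent.** A reader might see a conflict between Table 4 and the 7.3.2 text: "Target blood pressure for our study will be considered as 130/80 mm Hg for young individuals and 140/90 mm Hg for elderly". But 7.3.1 lists targets by method: office below 130/80 under 65 and below 140/90 from 65, home 135/85. As home readings drive titration, Table 4 plausibly uses the home counterpart of the office target. No contradiction is shown. The 7.3.2 text does not name its method, so a clarification is worthwhile.

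**Supporting data exist.** ABPM in all patients and outcome 4 are already planned. True, and this is why the fix is cheap; but nothing ties them to the reading of outcome 3.

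**Conclusion.** The point holds as a limit on interpretation. Only Group B has a written step-down rule, its main trigger is a pressure level, and controlled patients are eligible, so a difference in drug reduction can arise with no blood pressure effect of the programme. This rests on the protocol's text and not on the illustration. The size and sign of that component cannot be estimated from the protocol.

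The comparison is valid for the full strategy including its withdrawal rule. It does not show that nutrition or metabolic improvement reduced the need for drugs. It would go too far to conclude that the comparison is invalid, or that Group A must be given a step-down rule.

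Separately, Table 4's seven-day condition does not fit the five-day home schedule and needs correction. The primary endpoint and sample size are not affected.

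**What to change.** 1. **Objective 3 and outcome 3.** Add one or two sentences: the result estimates the effect of the full Twin Precision strategy including its medication-withdrawal protocol; it is reported beside concurrent ABPM and outcome 4 (new drugs and dose increases); and it supports no claim that nutrition or metabolic health reduced the drug requirement. Both companion measures are already collected. The cost is a narrower claim.
2. **Table 4.** Redefine the seven-day trigger so that it can be met under 7.5.2, for example seven consecutive scheduled reading-days, or daily readings during the assessment week. The second adds two reading-days in that week (7 − 5 = 2).
3. **7.3.2.** State that 135/85 is the home threshold and that 130/80 (140/90 from age 65) is the office target. This is wording only.

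A shared step-down rule in Group A is an option for the sponsor, not a required change. It would take the withdrawal rule out of the randomised contrast, but it alters the guideline comparator and may raise Group A's blood pressure, which is the primary endpoint. None of the three changes needs extra patients.
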